#### ***7.1.1.2 Reporting of Serious Adverse Events to Regulatory Authorities and Investigators***

All SAEs that are considered unexpected and related to the IP will be reported by QuintilesIMS as a 15-Day report to the regulatory authorities as applicable and to all participating Investigators. The SAEs that are considered unexpected, related to the study and are life-threatening or result in death will be reported by QuintilesIMS to the regulatory authorities as applicable, and to all participating Investigators as a 7-Day report. QuintilesIMS will ensure that all SAEs are reported to the appropriate regulatory authorities.

Investigators will be notified by QuintilesIMS of all SAEs that require prompt submission to their Institutional Review Board (IRB). Each Investigator must notify the IRB responsible for reviewing the study at their site of all 15-Day or 7-Day safety reports required by local regulations or IRB requirements and should provide written documentation of IEC notification for each report to QuintilesIMS. This study will comply with all local regulatory requirements and adhere to the full requirements of ICH Guideline for Clinical Safety Data Management, Definitions and Standards for Expedited Reporting, Topic E2.

#### ***7.1.1.3 Follow-Up of Adverse Events***

Any AEs observed from the time of informed consent signed up to the end of the study will be followed up to resolution. Resolution means that the patient has returned to a baseline state of health or the Investigator does not expect any further improvement or worsening of the AE or the patient is deemed lost to follow-up. All AEs that occur after the patient completed a clinical study should also be reported to AnaptysBio and/or QuintilesIMS within 30 days of the patient's last visit.

#### **7.1.2 Clinical Laboratory Evaluations**

Blood samples for hematology, clinical chemistry evaluations including serum pregnancy test, FSH, and serological assays, will be collected at the visits specified in [Table 4.1](#). A list of specific clinical laboratory evaluations is provided in [Table 7.1](#) below:

**Table 7.1 Clinical Laboratory Parameters**

Hematology	Clinical Chemistry	Virology	Urinalysis	Drugs of Abuse (Only at Screening)
Hematocrit Packed Cell Volume Hemoglobin Mean Cell Haemoglobin Mean Cell Hemoglobin Concentration Mean Cell Volume Platelet Count Red Blood Cell Count White Blood Cell Count Basophils Eosinophils Monocytes Neutrophils Lymphocytes Immunoglobulins (IgA, IgG, IgM, IgE, and IgD)	ALT Albumin ALP AST Bicarbonate Bilirubin (Total) Bilirubin (Direct) (only if Total is elevated) Calcium Chloride C-Reactive Protein Creatinine GGT Glucose Potassium Phosphate (Inorganic) Protein (Total) Sodium Troponin Urea  WOCBP Only - hCG levels Postmenopausal woman aged over 45 years with at least 1 year of amenorrhea only - FSH levels (only at Screening visit)	Hepatitis B Surface Antigen Hepatitis C Antibody HIV Antibody  TB Screening Quantiferon Gold® test (only at Screening visit)	Bilirubin Blood Glucose Ketones Leukocytes Nitrates pH Protein Specific gravity Urobilinogen  At discretion of Investigator based on urinalysis results Microbiology Urine Microscopy	Amphetamines Barbiturates Benzodiazepines Cocaine Marijuana/Cannabis Methadone Methamphetamine/ Ecstasy Morphine/Opiates Phencyclidine Tricyclic Antidepressants

Abbreviations: ALP = alkaline phosphatase; ALT = alanine transaminase; AST = aspartate aminotransferase; FSH = follicle stimulating hormone; GGT = gamma glutamyl transferase; hCG = human chorionic gonadotropin hormone; HIV = human immunodeficiency virus; TB = tuberculosis; WOCBP = women of childbearing potential.

The clinical laboratory tests will be reviewed for results of potential clinical significance, based on Investigator's discretion, at all time points throughout the study. The Investigator will evaluate any change in laboratory values. If the Investigator determines a laboratory abnormality to be clinically significant, it is considered a laboratory AE; however, if the abnormal laboratory value is consistent with a current diagnosis, it may be documented accordingly.

### 7.1.3 Vital Signs, Physical Findings, and Other Safety Assessments

Vital signs will be measured, and physical examinations and ECGs will be performed at the time points indicated in the Schedule of Events (Table 4.1).

Vital signs include pulse rate, respiratory rate, body temperature, systolic BP, and diastolic BP. The physical examination includes evaluation of general appearance, head, eyes, ears, nose, and throat, and pulmonary, cardiovascular, gastrointestinal, renal/genitourological, endocrine (including thyroid), musculoskeletal/spinal, lymphatic, and dermatologic systems.

During the BPCFC, clinical evaluations using the OFC Symptom Scoring Assessment Tool and vital signs will be done before starting the initial placebo challenge, after completion of the final placebo challenge, before starting the initial peanut challenge, upon completion of the final peanut challenge, and 2 hours after completion of the final peanut challenge. Full physical examinations will be performed before starting the initial placebo food challenge and upon completion of the final peanut challenge (prior to discharge), and more frequent if deemed appropriate by the Investigator on the challenge day.

A standard 12-lead ECG will be performed by a qualified physician or nurse. The following parameters will be documented: HR, PR interval, QRS interval, QT interval, and QTc interval. The ECG will be reviewed by the Investigator or an authorized representative who is experienced in the evaluation of ECGs and assessed for clinical significance.

#### **7.1.4 Safety Monitoring**

There is no data monitoring committee for this study.

Timely and complete reporting of safety information assists the Sponsor in identifying any untoward medical occurrence, thereby allowing: (1) protection of safety of study patients; (2) a greater understanding of the overall safety profile of the IP; (3) recognition of dose-related IP toxicity; (4) appropriate modification of study protocols; (5) improvements in study design or procedures; and (6) adherence to worldwide regulatory requirements.

### **7.2 Pharmacodynamics**

For circulating leukocytes, whole blood (2 mL) samples will be taken in ethylenediaminetetraacetic acid (EDTA) Vacutainer (2 mL). Differential WBC counts in whole blood will be measured to monitor the circulating leukocyte populations. The sample for leukocytes will be obtained as part of the hematology safety laboratory panel at screening, Day 2, and Day 45/ET. On Day 5 and Day 15, sample for leukocytes will be collected separately as there is no safety laboratory assessments on Day 5 and Day 15.

For circulating cytokines, whole blood samples (total 7.5 mL) will be taken in serum separator tube (SST). Circulating cytokines measured will include, but may not be limited to, IL-4, IL-5, IL-9, IL-13, IL-33, and sST2 (see lab manual for detailed collection and processing instructions).

For the ex vivo peanut antigen challenge, whole blood (10 mL) samples collected from Stanford University patients will be taken in 10 mL SST vacutainer. The whole blood peanut response assay (ex vivo) will measure cytokine levels released from pathogenic T cells, and should include, but may not be limited to, IL-4, IL-5, IL-9, IL-13, and IL-33.

The serum and whole blood biomarker time points are presented in [Section 18.0 \(Appendix 2\)](#). The actual date and time of the sample collection will be recorded in the patient's eCRF. The details of blood sample collection, sample tube labelling, sample preparation, storage, and shipping procedures will be described in a separate laboratory manual.

The measurement of circulating leukocytes and circulating cytokines will be performed using validated assay methods. The measurement of cytokine levels released from pathogenic T cells (ex vivo peanut response assay) will be performed using an exploratory assay method developed by [REDACTED]. The analytical methods used to measure these PD endpoints will be described in a separate bioanalytical report.

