## 1.0 LIST OF ABBREVIATIONS AND DEFINITIONS OF TERMS

Abbreviation	Definition
AD	Atopic dermatitis
ADR	Adverse drug reaction
AE	Adverse event
ANCOVA	Analysis of covariance
BMI	Body mass index
BP	Blood pressure
CI	Confidence interval
C max	Maximum observed concentration
CV	Coefficient of variation
BPCFC	Blind placebo-controlled food challenge
ECG	Electrocardiogram
eCRF	Electronic case report form
EDC	Electronic data capture
EpiPen	Epinephrine
EOS	End of Study
ET	Early Termination
FSH	Follicle stimulating hormone
GCP	Good Clinical Practice
gCV	Geometric coefficient of variation
GINA	Global Initiative for Asthma Assessment
Gmean	Geometric mean
GMP	Good Manufacturing Practice
hIL-33	Human interleukin-33
HR	Heart rate
ICF	Informed Consent Form
ICH	International Council for Harmonisation
ICU	Intensive care unit
IgE	Immunoglobulin E
IL	Interleukin

IP	Investigational product
IRB	Institutional Review Board
IV	Intravenous(ly)
LLOQ	Lower limit of quantification
mAb	Monoclonal antibody
MAD	Multiple ascending dose
MedDRA	Medical Dictionary for Regulatory Activities
n	Sample size or number of observations
OFC	Oral Food Challenge
PD	Pharmacodynamic
PI	Principal Investigator
PK	Pharmacokinetic
SAE	Serious adverse event
SAD	Single ascending dose
SAP	Statistical analysis plan
SAS	Statistical analysis system
SC	Subcutaneous
SD	Standard deviation
SOP	Standard operating procedure
SST	Serum separator tube
ST2	Surface receptor 2
$t_{1/2}$	Terminal half-life
TEAE	Treatment emergent adverse event
Th2	T helper-2
$t_{max}$	Time to maximum observed concentration
U.S.	United States
WBC	White blood cell

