**Table 6.1 Blood Volume Sampling During Each Visit**

Visits	Screening	Day 1 Predose	Day 1 Predose (PK)	Day 1 (0.5H) (PK)	Day 1 (EOI) (PK)	Day 1 (EOI 3H) (PK)	Day 2	Day 5	Day 14	Day 15/16	Day 45
Stanford Univ. Only Total blood volume sampled during each visit (mLs)	up to 41 (31-41) a	up to 22 (12-22) a	5	5	5	5	34	25.5	12	15.5	17
Total blood volume sampled during each visit (mLs)	31	12	5	5	5	5	24	15.5	12	15.5	17

Abbreviation: EOI = actual time of end of infusion; PK = pharmacokinetics

a. The blood sample for ex vivo peanut challenge assay (approximately 10 mL) can be collected either at screening or on Day 1. Based on this sample collection, blood volume required at screening and Day 1 will vary.

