### **7.3 Pharmacokinetics**

Samples (5 mL) of whole blood will be obtained in a 5 mL Vacutainer® SST for the determination of ANB020 in human serum. Samples will be collected according to the schedule presented in [Section 18.0 \(Appendix 2\)](#). Approximately 40.0 mL of whole blood will be obtained from each patient for PK assessments during the study.

If a patient refuses blood collection for PK analysis, this will not be considered a protocol violation as the PK analysis is a secondary objective.

The actual date and time of dosing and of the blood sample collection will be recorded in the patient's eCRF. The details of blood sample collection, sample tube labelling, sample preparation, storage, and shipping procedures will be described in a separate laboratory manual.

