Programming Note (not part of table): Sort by patient number, visit, date and time of collection Present all the visits where assessment done

Document: \\ieedc-nas01a\biosdata\AnaptysBio\ANB020\CYA74393\Biostatistics\Documentation\SAP\Final\2018-02-07

Author: [REDACTED]

Version Number: Final 1.0

Version Date: 07Feb2018

Listing 16 2 8 10
Ex vivo Peanut Challenge Assay for Cytokines Released from T-cells (Whole Blood) - Safety Analysis Set

Patient No / Treatment	Visit	Blood Sample Collected? If No, Reason	Date and Time of Collection	Time Stimulated (Hours)	Date and Time of Sample Run	Analyte (Unit)	Value	Change from Baseline	Relative Change from Baseline
XXX/XXX	Baseline	Yes	DDMMYY	hh:mm	DDMMYY	xxx (unit)	xxxx		

Day 2
 
-----
									

Day 5
 
-----
									

Baseline
 
-----
									

Day 5
 
-----
									

-----
 
-----
									

Programming Note (not part of table): Sort by patient number, analyte, visit, date and time of collection Present all the visits where assessment done Present all analytes

Document: \\ieedc-nas01a\biosdata\AnaptysBio\ANB020\CYA74393\Biostatistics\Documentation\SAP\Final\2018-02-07

Author: [REDACTED]

Version Number: Final 1.0

Version Date: 07Feb2018

Listing Shells

AnaptysBio Inc.
PROTOCOL ANB020-003
Page 40 of 41

Listing 16 2 8 11 1
Subjects Excluded from the Pharmacokinetic Analysis Set

Patient No / Treatment	Reason(s) for exclusion

Document: \\ieedc-nas01a\biosdata\AnaptysBio\ANB020\CYA74393\Biostatistics\Documentation\SAP\Final\2018-02-07

Author: [REDACTED]

Version Number: Final 1.0

Version Date: 07Feb2018

Listing Shells

AnaptysBio Inc.
PROTOCOL ANB020-003
Page 41 of 41

Listing 16 2 8 11 2
Data Excluded from the Pharmacokinetic Analysis Set

Patient No / Treatment	Data excluded	Reason(s) for exclusion
---------------------------	---------------	-------------------------

Document: \\ieedc-nas01a\biosdata\AnaptysBio\ANB020\CYA74393\Biostatistics\Documentation\SAP\Final\2018-02-07

Author: [REDACTED]

Version Number: Final 1.0
Version Date: 07Feb2018

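### Protocol Section 7.2 names a serum separator tube for the ex vivo whole-blood peanut stimulation sample; taken literally, this would compromise that exploratory endpoint

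*Protocol*

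**What the plan says.** Protocol Section 7.2 sets out three pharmacodynamic samples. For the ex vivo peanut antigen challenge it says that "whole blood (10 mL) samples collected from Stanford University patients will be taken in 10 mL SST vacutainer". The abbreviation list in Section 1.0 expands SST as "Serum separator tube". The sentence after the tube instruction describes the test: "The whole blood peanut response assay (ex vivo) will measure cytokine levels released from pathogenic T cells". Listing 16.2.8.10 in the SAP listing shells has a column for the hours of stimulation, so the sample is expected to be incubated with a stimulus after collection.

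The same section puts the 7.5 mL circulating-cytokine sample in an SST and the 2 mL leukocyte sample in an EDTA tube. Section 7.3 says of PK: "Samples (5 mL) of whole blood will be obtained in a 5 mL Vacutainer® SST for the determination of ANB020 in human serum".

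On volume, the footnote to Table 6.1 says: "The blood sample for ex vivo peanut challenge assay (approximately 10 mL) can be collected either at screening or on Day 1". Table 4.1 and Appendix 2 add ex vivo samples on Day 2 and Day 5. They call the sample whole blood and name no tube.

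Section 7.2 leaves preparation and handling to a separate laboratory manual and the analytical methods to a bioanalytical report. Neither was supplied. The ex vivo method is described as exploratory, and its developer is redacted.

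**The concern.** The tube does not fit the sample. A serum separator tube is meant to yield serum, which is what remains once blood has clotted and the cells have been removed. An assay that adds antigen to whole blood and reads the cytokines that T cells release needs those cells free and responsive. The protocol names the tube outright, so this is an operative collection instruction and not a detail left open.

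If the instruction were followed, the baseline, Day 2 and Day 5 samples would all be affected, so both the covariate and the responses in the planned model would be compromised. The tube is the same in both arms, so it would not by itself favour either arm. The harm would be to interpretation: cytokine readings might not reflect an antigen-specific response, and a finding of no difference could not be read as absence of a drug effect. The draws are tied to fixed times after the infusion and cannot be repeated later.

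**Working it through.** No sample-size or power formula applies. The check compares each tube with what is measured, and then tests whether the stated blood volumes leave room for another tube.

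**Tube against measurement (Protocol Sections 7.2 and 7.3)**

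| Sample | Tube named | What is measured | Fit |
|---|---|---|---|
| Circulating cytokines, 7.5 mL | SST | Serum analytes | Yes |
| ANB020 concentration, 5 mL | SST | Serum drug level | Yes |
| Leukocytes, 2 mL | EDTA | Cells in whole blood | Yes |
| Ex vivo peanut challenge, 10 mL | SST | Cytokines released by T cells in whole blood | No |

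Only the ex vivo row pairs a serum tube with a cell-based test. No other place in the protocol or SAP names a different tube for it, or says that the blood is anticoagulated or transferred after the draw.

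**The plan's volume figures (Section 6.2.1 and Table 6.1)**

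- Stanford, with the first ex vivo sample taken at screening: 41 + 12 + 5 + 5 + 5 + 5 + 34 + 25.5 + 12 + 15.5 + 17 = 177 mL. This matches the stated 177 mL.
- Other sites: 31 + 12 + 5 + 5 + 5 + 5 + 24 + 15.5 + 12 + 15.5 + 17 = 147 mL. This matches the stated 147 mL.

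**Is there a second Stanford-only tube?**

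- Difference by visit: 41 − 31 = 10 mL at screening (or 22 − 12 = 10 mL on Day 1 if the sample is moved), 34 − 24 = 10 mL on Day 2, and 25.5 − 15.5 = 10 mL on Day 5. It is zero at every other visit.
- Total: 177 − 147 = 30 mL = 3 × 10 mL.

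The ex vivo draws account for all of the Stanford-only blood. The tables therefore leave no volume for an additional anticoagulated tube beside the SST. This does not show which tube is used in practice. It shows only that the protocol does not provide for two.

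**Size**

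- Per Stanford patient: 3 samples, 30 mL, or 30/177 = 17% of the blood drawn.
- Ceiling: 3 × 20 = 60 samples if all 20 patients were at Stanford. The synopsis allows up to 3 centers, and the split by site is not given, so the number may be lower.

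**The case against.** The strongest reply is that this may be no more than a misnamed tube. The laboratory manual governs preparation and handling, and it has not been seen. The assay is run for one site only, and the amendment log explains that it was developed for the local laboratory. Staff there may already use a suitable tube whatever Section 7.2 says. The documents do not state the tube's additive, when antigen is added, or how the blood is handled after the draw. That serum separator tubes clot blood is general laboratory knowledge, implied by the name but not stated in the text.

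Most of this stands, and it limits how far the point can go. A reader might infer that the assay cannot measure T-cell cytokine release and that the endpoint is lost. The documents do not support that, because they cannot separate a wrong name from a wrong procedure. A reader might also infer that a particular anticoagulant is required. Heparin is mentioned nowhere in either document, and the choice belongs to the laboratory that developed the method.

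The reply does not remove the mismatch. If the manual repeats the protocol, the instruction is unsuitable for the assay. If the manual names another tube, the two documents conflict, and a correctly drawn sample departs from the protocol as written. Section 7.2 needs correcting in either case.

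**Conclusion.** Section 7.2 is wrong as written. It directs a whole-blood stimulation sample into a serum tube, against the pattern of tubes used elsewhere in the protocol. Taken literally, this would compromise one exploratory endpoint at one site: three 10 mL draws per Stanford patient, with 60 samples as an upper bound.

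Two wider readings go too far:

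- SAP Section 20 also compares circulating cytokines and leukocytes, whose tubes fit their measurements. Only its ex vivo part is exposed.
- Protocol Section 4.2 states an aim to provide evidence on mechanism and on a short-term clinical outcome, but it does not name this assay. Serum cytokines and leukocytes also bear on mechanism. The oral challenge, which gives the clinical outcome, is unaffected, as are safety and PK.

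The conclusion rests on two assumptions: that SST carries the meaning given in the abbreviation list, and that such a tube yields clotted blood. Confidence is high that the text is mismatched. Whether any sample was or would be spoiled cannot be judged without the laboratory manual and the assay method.

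**What to change.** In Protocol Section 7.2, for the ex vivo assay only, replace the SST with the anticoagulated whole-blood tube specified by the assay's developing laboratory, after confirming it with that laboratory. Make the laboratory manual agree. Keep SSTs for serum cytokines and PK. If ex vivo samples have already been drawn, document which tube was used for each before analysing them.

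The cost is one phrase in the protocol, a check of the manual and possibly one item in the collection kit. Visits and blood volumes do not change.

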### **7.3 Pharmacokinetics**

Samples (5 mL) of whole blood will be obtained in a 5 mL Vacutainer® SST for the determination of ANB020 in human serum. Samples will be collected according to the schedule presented in [Section 18.0 \(Appendix 2\)](#). Approximately 40.0 mL of whole blood will be obtained from each patient for PK assessments during the study.

If a patient refuses blood collection for PK analysis, this will not be considered a protocol violation as the PK analysis is a secondary objective.

The actual date and time of dosing and of the blood sample collection will be recorded in the patient's eCRF. The details of blood sample collection, sample tube labelling, sample preparation, storage, and shipping procedures will be described in a separate laboratory manual.

### **Bioanalysis**

The measurement of the concentrations of ANB020 will be performed using a validated assay method. The analytical methods used to measure concentrations of ANB020 will be described in a separate bioanalytical report.

### **7.4 Efficacy**

Primary and secondary efficacy endpoints included difference in total cumulative tolerated peanut dose during BPCFC between baseline and post-treatment with ANB020 or placebo on Day 14 and OFC symptom scores on Day 14.

Exploratory efficacy endpoints included difference in total cumulative tolerated peanut dose during BPCFC between baseline and post-treatment with ANB020 or placebo on Day 45 and OFC symptom scores on Day 45.

The oral BPCFC will be performed according to the PRACTALL guidelines and Symptoms will be monitored using the OFC Symptom Scoring Assessment Tool. Refer [section 6.1.1](#) and [Appendix II](#) for more details.

## **7.5 Health Outcomes**

Not applicable.

## **7.6 Pharmacogenetics**

Not applicable.

## **7.7 Appropriateness of Measurements**

All safety assessments used in this study are standard, i.e., widely used and generally recognized as reliable, accurate, and relevant.

## **8.0 QUALITY CONTROL AND QUALITY ASSURANCE**

According to the Guidelines of Good Clinical Practice (GCP) (CPMP/ICH/135/95), QuintilesIMS is responsible for implementing and maintaining quality assurance and quality control systems with written SOPs.

Quality control will be applied to each stage of data handling.

The following steps will be taken to ensure the accuracy, consistency, completeness, and reliability of the data:

- Central laboratories for clinical laboratory parameters.
- Center Qualification visit.
- Center Initiation visit.
- Early center visits post-enrollment.
- Routine center monitoring.
- Ongoing center communication and training.
- Data management quality control checks.
- Continuous data acquisition and cleaning.
- Internal review of data.
- Quality control check of the final clinical study report.

In addition, AnaptysBio and/or QuintilesIMS Clinical Quality Assurance Department may conduct periodic audits of the study processes, including, but not limited to study center, center visits, central laboratories, vendors, clinical database, and final clinical study report. When audits are conducted, access must be authorized for all study related documents including medical history and concomitant medication documentation to authorized AnaptysBio's representatives and regulatory authorities.

